**Research Abstract:**

There is an immense need for low-cost colostomy appliances among ostomy patients living in low-income countries in Sub-Saharan Africa. There are an estimated 1.2 million new cases globally of colorectal cancer annually (1). Additionally, instances of colorectal cancer and the need for colostomies is increasing in Sub-Saharan Africa at an annual rate of up to 6.8% in certain countries (2).

Without access to colostomy products, low-income patients often resort to handmade solutions, such as taping a plastic bag to one's stoma. However, these makeshift solutions are not safe, odor-proof, or leak-proof, which lead to a decreased quality of life for these individuals. To combat this problem, we have developed LowCostomy: a highly affordable (<5 cent) colostomy appliance that capitalizes on utilizing low-cost, recycled materials in addition to a novel, all-natural formula of beeswax and pine resin that replaces the expensive adhesive material found in traditional adhesives for colostomy appliances. Existing skin-care products that separately contain beeswax and pine resin have been proven to be safe, non-toxic, and non-corrosive (7, 8,9, 10); however, there are still potential risks for rash, irritation, infection and other topical reactions upon the combination of these two substances.

The purpose of this study is to investigate the safety of a beeswax-pine resin mixture as it acts as a buffer between the patient's peristomal skin and the colostomy appliance. Rather than testing the entire LowCostomy system, this study will focus solely on the safety of the beeswax-pine resin buffer. The effect of having the beeswax-pine resin buffer adhered to the skin on the abdomen over a one-week period will be analyzed independently by a licensed physician, with an emphasize on assessing changes in color, texture, and overall skin health using the Draize skin irritation test. Subject surveys will also be utilized to record subject experiences and will include quantitative sections like the 5-D itch scale. Compiled results will be analyzed by an accredited statistician.

**Study Objective:**

To determine whether the beeswax-pine resin mixture used in the LowCostomy buffer can be safely applied to intact human abdominal skin for the duration of a one-week period.

## Standard Research Summary

### Purpose of the Study:

The objective of the study is to determine whether the beeswax-pine resin mixture used as part of the LowCostomy appliance as a buffer can be safely applied to human skin. "Safe" is defined as no greater external skin irritation or injury compared to standard commercially available ostomy appliance products such as the Hollister Adapt Seal barrier ring, used in a similar manner to the beeswax-pine resin buffer as part of the LowCostomy appliance (3). The hypothesis to be tested is that the beeswax-pine resin mixture is safe for topical application to human skin.

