Photo documentation with the dedicated camera will occur on Day 1 at the initial screening visit as noted above, as well as Day 7. Photos will be collected by trained personnel in a private room without windows. A licensed physician will grade the blinded photos, indicating the appropriate level of skin irritation and rash by utilizing the Draize skin scoring system. Subjects will be given contact information to report any skin irritation or other adverse events during the 7-day trial period. Should a severe skin reaction occur, subjects will be directed to the licensed physician reviewer or a consult with a dermatologist. All subjects will record their experience through a RedCap survey which will include the 5D itch scale. After quantitative values have been assigned to each of the blinded photos, data visualizations will be created, and appropriate statistical analysis will be completed to evaluate for significant differences between each of the samples applied to subjects' skin.

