**Risk/Benefit Assessment:**

The main risk of the study is a reaction or skin irritation caused by the beeswax-pine resin mixture. This could include an allergic reaction, local skin irritation, redness, itchiness, or in severe cases blistering. Based on background research of existing beeswax-pine resin products, it has been hypothesized that a reaction is unlikely, but still possible. If a reaction occurs that is too uncomfortable to continue the study for the entire 7 days, the subject may stop early, and the reaction will be noted. The risks of the study are not being borne by the likely beneficiaries. The test subjects will likely not gain any health benefits from participating in the study; such subjects are not colostomy patients and hence not the target consumers of the LowCostomy appliance. Further, if an ostomy patient happens to participate in the study, he/she will likely return to the use of higher-priced medical-grade colostomy appliances without the use of the beeswax-pine resin mixture as the LowCostomy device will be marketed to populations in low-resource settings. The analysis expected to result from the tests is more valuable to the target low-income patients of Sub-Saharan Africa, who would be using this mixture on their skin. This is the main purpose of providing a monetary incentive to American patients who participate.

The loss of privacy and confidentiality is an additional risk. However, every reasonable effort will be made to limit breaches of privacy and confidentiality.

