**Data Analysis and Statistical Considerations**

Data from subjects who successfully complete the seven-day study will be used for analysis. The photos from Day 1 and Day 7 will be reviewed by the licensed physician using the Draize skin scoring system. Subjects will fill out a survey of their experiences of wearing the beeswax-pine resin adhesive. The 5-D itch scale will be used to quantify subjective experiences. All photos included in the dataset will be blinded before a licensed physician quantitatively indicate the level of skin irritation. Only the data of subjects who completed data collection for the entire 7-day duration will have their results quantified. Statistical tests will be completed on the results to draw conclusion about whether the beeswax-pine resin samples, in comparison to our control, caused skin irritation.

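### The definition of 'safe' includes injury, but the planned comparison concludes on irritation in 7-day completers only, so infection, healed injury and injury that ends participation are never set against the control ring

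*Protocol*

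**What the plan says.** - **Criterion.** Protocol, Purpose of the Study, defines safe as "no greater external skin irritation or injury compared to standard commercially available ostomy appliance products". It then states: "The hypothesis to be tested is that the beeswax-pine resin mixture is safe for topical application to human skin". Injury relative to the commercial ring is therefore part of what is to be tested.
- **Outcomes.** Under Design and Procedures, a physician grades blinded photographs, "indicating the appropriate level of skin irritation and rash by utilizing the Draize skin scoring system". The Research Abstract describes the task more broadly, as "assessing changes in color, texture, and overall skin health using the Draize skin irritation test". Photographs are taken on Day 1 and Day 7 only. Data Analysis and Statistical Considerations adds: "The 5-D itch scale will be used to quantify subjective experiences".
- **Comparison.** The same section says that the tests will show whether the beeswax-pine samples, "in comparison to our control, caused skin irritation". Injury is not mentioned there.
- **Injury foreseen.** Risk/Benefit Assessment lists "local skin irritation, redness, itchiness, or in severe cases blistering". A subject who finds a reaction too uncomfortable may stop, and the reaction is noted. Data and Safety Monitoring adds infection, and ends the subject's seven days at any sign of infection or another adverse effect.
- **Analysed set.** Data Analysis and Statistical Considerations quantifies only subjects with data for the full seven days.

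**The concern.** The criterion has two parts, and the stated conclusion speaks to one of them. The protocol itself expects that blisters and infections may occur, and handles them as safety matters: they are noted, reviewed by a physician, or lead to stopping. No section sets their frequency under a beeswax ring against their frequency under the control ring.

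The completer rule turns a difference of wording into a possible wrong answer. An injury serious enough to end participation removes that subject from the quantified data. Injuries confined to a test ring could therefore leave no trace in the result on which the safety claim rests. The claim is meant to support use on peristomal skin, where an injury matters more than a small shift in redness.

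**Working it through.** The protocol gives no figure for this point. It states a sample of 50 without a margin, power or expected event rate, so there is nothing to reproduce. The check is one of consistency, followed by an illustration of size.

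**1. Follow each kind of injury through the stated rules.**

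| Event under a ring | In the Day 7 photograph of an analysed subject? | Compared with control? |
|---|---|---|
| Blister visible on Day 7, subject completes | Yes | Possibly, through the Draize grade |
| Injury healed by Day 7, subject completes | No; there is no photograph between Day 1 and Day 7 | No |
| Infection | Subject is stopped under Data and Safety Monitoring, so not a completer | No |
| Any injury that leads to an early stop | Subject is not a completer | No |

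Only the first row can reach the comparison, and it does so as part of an irritation grade, not as a separate injury outcome.

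**2. Illustrate the effect of the completer rule.** The input from the protocol is 50 subjects, each wearing all three rings. The assumption is that k subjects have an injury under one beeswax ring, none has one under the control ring, and all k stop early. The analysed set is then 50 − k, with 0 against 0 injuries. With all subjects kept, the exact two-sided paired (sign) test for k discordant subjects, all in one direction, gives p = 2 × 0.5^k.

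| k (assumed) | Completers, 50 − k | Injuries seen among completers | p with all 50 counted |
|---|---|---|---|
| 3 | 47 | 0 against 0 | 2 × 0.5^3 = 0.25 |
| 5 | 45 | 0 against 0 | 2 × 0.5^5 = 0.0625 |
| 6 | 44 | 0 against 0 | 2 × 0.5^6 = 0.031 |
| 8 | 42 | 0 against 0 | 2 × 0.5^8 = 0.0078 |

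The p-values are for one beeswax ring against control, without adjustment for there being two such rings.

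**3. What 50 subjects can show about injury.** With no injury in 50, the one-sided 95% upper limit u solves (1 − u)^50 = 0.05, so u = 1 − 0.05^(1/50) = 0.058, or 5.8%. An injury comparison of this size is therefore descriptive. Six discordant subjects, all in one direction, are needed for p < 0.05.

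**The case against.** The strongest reply is that the protocol does provide for adverse skin reactions by site. Design and Procedures has the three application areas marked, puts a measuring device in each photograph so that such reactions can be quantified, and plans to look for differences between the samples. Risk/Benefit Assessment places blistering at the severe end of a reaction, and the Abstract gives the Draize assessment a wide scope. This stands for anything visible on Day 7 in a completer. A reader might infer that no injury is recorded by ring, or that half of the definition goes unexamined; the documents do not support either.

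A reader might also infer that a few blisters would be diluted in an average grade. That assumes a comparison of means, and the protocol names no summary measure. Nor can it be said that itch is compared between rings: the survey is tied to wearing the beeswax-pine adhesive, and no section says it is scored per ring.

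Finally, a statistical analysis plan could add an adverse-event table. That is fair for tests and layout. But the protocol itself fixes the definition, the graded outcome, the conclusion and the analysed set, and these do not agree. A plan that followed them would inherit the gap. Attribution to a site must also be collected while the rings are worn; it cannot be added at analysis.

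The completer rule is a weakness in its own right and accounts for much of the consequence here. Correcting it alone would still leave a conclusion that does not mention injury, and no comparison for infection or healed injury.

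**Conclusion.** The point holds in a limited form. Followed exactly, the protocol could declare the mixture safe while infections, healed injuries and injuries that ended participation had all occurred under a beeswax ring. Those three groups are never compared with the control, and the last leaves the analysed data by rule. Injury still visible on Day 7 in a completer may be captured.

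The size cannot be derived from the protocol, which gives no expected injury rate. The counts above are assumptions that show the mechanism, and they also limit what may be claimed for the remedy: three injuries against none would be worth reporting but would give p = 0.25. The conclusion rests on reading the stopping and completer rules as written. If few subjects were injured or stopped, the effect on the result would be small. It should be corrected because it bears on what the trial may conclude and costs little.

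**What to change.** Amend Data Analysis and Statistical Considerations along these lines: *For every subject who had rings applied, including those who stop early, each blister, skin breakdown or infection will be recorded by ring site. The number of sites with any injury will be reported for each ring with an exact confidence interval, alongside the control site of the same subject. The safety conclusion will rest on both irritation and injury.*

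This costs one site field on the event report and one small table. No rule on stopping or care of subjects changes. The drawback is that the injury result will be descriptive with about 50 subjects, and the safety claim will carry a visible upper limit even if no injury occurs.

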### Background and Significance:

Colorectal cancer plagues approximately 1.2 million people annually as the third most common cancer worldwide, causing 600,000 deaths per year (1,3). The incidence of colorectal cancer in Sub-Saharan Africa is estimated to be around 4.04 per 100,000 population with this value increasing (3). In fact, incidence of colorectal cancer in Sub-Saharan Africa is increasing annually at an average rate of 4% (2). Common treatment for those diagnosed with any stage of colorectal cancer is to receive surgical intervention, commonly segmental colonic resection with an end colostomy. Unfortunately, colorectal cancer is only one factor contributing to the rising number of colostomy patients; trauma patients with intestinal obstruction via intestinal volvulus is another factor that leads to the increased number of colostomy patients seen in Sub-Saharan Africa (4, 11). A study performed in Ethiopia demonstrated that of the 33.95 surgical admissions per 100,000 population per year, 10.3% were due to intestinal obstructions (4). Despite the increasing number of cancer and intestinal trauma patients who receive colostomies, there has yet to be an affordable colostomy appliance created for the low-to-medium income patients for post-surgical maintenance care in low-to-medium resource countries. This is precisely the demand that the LowCostomy colostomy appliance aims to meet.

All colostomy patients deserve high-quality, affordable colostomy appliances that enable them to continue their daily lives with the least amount of disruption from stool leakage, foul odor and skin irritation. However, high-quality colostomy appliances commercially available today are expensive and unavailable to those in less developed countries. For many colostomy patients in Sub-Saharan Africa, spending \$6-10 on a high-quality colostomy appliance that only lasts two to three days inflicts an immense financial burden (5). In most cases, the cost of routinely purchasing high-quality colostomy appliances that last only a few days exceeds the average income per year for people in Sub-Saharan Africa. The high cost and lack of access forces many patients in Sub-Saharan Africa to resort to creating homemade solutions with rubber bands, tape, miscellaneous bags, and other available materials. Such methods often cause leakage, foul odors, discomfort, and further health complications which disrupt the daily life activities and overall quality of life for a colostomy patient. Surgical procedures impact one's ability to monetarily provide for themselves and their families; in fact, a staggering economic productivity loss of \$12.3 trillion due to poor provision of surgical care in low-to-middle income countries was projected for the period between 2015 and 2030 (6). With major health disparities among mortality rates and treatment options/availability, action must be taken to remedy the lack of healthcare equity in low-resource areas (1, 4). With these shortcomings in mind, the LowCostomy appliance is designed to improve the quality of life for colostomy patients in low-resource settings.

Despite the increase in demand for colostomy products, such supplies are still cost prohibitive; the high cost of colostomy appliances largely stems from the fact that companies are continually trying to outcompete each other's novel adhesive formulas. The research and development involved in this endeavor in turn increases the prices of colostomy products. With the effort to mitigate the cost of

effective adhesives, we evaluated various adhesive formulas that had the potential to be inexpensive and readily available for those in Sub-Saharan Africa. After various stages of testing, we formulated a mix of beeswax and pine resin that could replace the high-cost adhesive of most colostomy products on the market today. Beeswax was chosen because of its high availability and low cost in Sub-Saharan Africa; the pine resin is also an all-natural substance readily available that adds a more adhesive quality to the beeswax appliance-stoma buffer used in the LowCostomy system. Beeswax was not only chosen for its high availability and low cost, but beeswax is known to have antiseptic properties, making it beneficial for the peristomal skin which is prone to infection if skin irritation occurs.

The concept of being environmentally friendly was another significant aspect that went into the design of the LowCostomy appliance. A typical colostomy appliance is discarded after a few days' use. Additionally, many countries in Sub-Saharan Africa are already dealing with plastic pollution, resulting in these countries adopting a plastic bag ban. To avoid these conflicts, the LowCostomy appliance was designed to be made completely of recycled material, excluding the beeswax-pine buffer. Being composed of recycled material not only creates an environmentally friendly product, but it also provides a way for the appliance to be low cost. Colorectal cancer and intestinal trauma rates in Sub-Saharan Africa are high, and there are not adequate, low-cost solutions for post-surgical care. With this problem in mind, the LowCostomy appliance's purpose is to improve the quality of life of all patients, regardless of socioeconomic status. However, a major component of the system has not yet been tested for safety: the beeswax- pine resin buffer. Thus, this study will aim to determine the safety of beeswax and pine resin as applied to the skin.

#### **Design and Procedures:**

The purpose of this study is to examine the safety of the LowCostomy appliance's peristomal adhesive interface composed of a mix of beeswax and pine resin. Since this study is not directed at analyzing the efficacy of the entire LowCostomy system, only the beeswax mixture will be tested against test subjects' skin. Upon consultation with ostomy nurses, the peristomal skin was determined to be comparable to normal abdominal skin. Thus, rather than recruiting colostomy patients, the subject pool will include any willing healthy adults with age +/>>18 years (n=50). This subject pool must be heterogeneous in terms of ethnicity which ensures that a broad range of skin colors are being tested with the aim of removing bias toward a certain type or color of skin. The goal is to recruit 50% of subjects who self-identify as having a medium to dark skin tone and 50% who self-identify as having with a light skin tone. Subjects will be given \$50 as compensation.

Each study subject will be tested with two thin rings of the beeswax-pine resin formula—one being a domestic beeswax-pine sample while the other ring will be a Tanzanian beeswax-pine sample. Using both a domestic and international sample, we can test whether regional differences in these products might yield significantly different results. Such beeswax-pine samples will be tested alongside a control adhesive in the form of Hollister's AdaptTM Barrier Rings. The length of the study will be 7 days. The beeswax-pine ring will be created to match the dimensions of the control (width: 4.5 mm, outer diameter: 48 mm). The beeswax-pine buffer will be composed of the same beeswax-pine resin ratio that will be used in the LowCostomy appliance's overall design. Such tests will be performed on the subjects' abdomen. Prior to application, a licensed physician will record observations concerning the condition of the abdominal skin including color, odor, texture, and hygiene. Pictures will be obtained for documentation purposes as well using a Nikon D5600, 24.2M pixel camera. During picture taking we will limit identification by choosing an area of skin with limited identifying marks or tattoos. The camera will automatically date stamp the picture however, there will be no other identifiers captured. A single dedicated camera will be used for all photos. At the screening visit on Day 1, a member of the research team will obtain a current medication

list and a medical history regarding known pre-existing skin conditions and history of skin reactions to elements of the study and control adhesive rings, to validate that there are no additional associated risks with participating in this study. If the area of application is too hairy to obtain a clear view of the skin, the healthcare professional will shave the pertinent area. The three areas of application will be marked with a medical marker to ensure even and consistent placement of the samples. A measurement device will be included in each picture for documentation and quantification of adverse skin reactions. The control ring will be applied according to the manufacturer's instructions; the beeswax-pine rings will be placed in a similar fashion but in addition, will need to be massaged against the skin to build friction and heat, allowing for a more effective adhesion. To fully seal the rings with the skin, Tegaderm will be placed over the rings, which allows the study subject to shower over the 7-day period with minimal interference with the study results. If the initial adhesives are not able to endure the full 7 days due to adhesive or application failure, such results will be noted and excluded from final analysis.

Each subsequent day after the initial placement of the samples, the subject will be asked to remove the tegaderm and the three adhesive rings briefly for less than 20 minutes, then promptly reapply in the exact same location with new tegaderm. The act of daily removal and reapplication of the samples will simulate

the typical routine of colostomy patients as they remove and reapply their ostomy products.

Twenty-four pieces of tegaderm will be provided per subject for the purpose of reapplying the samples. During the education session, subjects will be shown how to properly apply tegaderm over the three samples. Subject participation ends at Day 7.

Photo documentation with the dedicated camera will occur on Day 1 at the initial screening visit as noted above, as well as Day 7. Photos will be collected by trained personnel in a private room without windows. A licensed physician will grade the blinded photos, indicating the appropriate level of skin irritation and rash by utilizing the Draize skin scoring system. Subjects will be given contact information to report any skin irritation or other adverse events during the 7-day trial period. Should a severe skin reaction occur, subjects will be directed to the licensed physician reviewer or a consult with a dermatologist. All subjects will record their experience through a RedCap survey which will include the 5D itch scale. After quantitative values have been assigned to each of the blinded photos, data visualizations will be created, and appropriate statistical analysis will be completed to evaluate for significant differences between each of the samples applied to subjects' skin.

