#### **Selection of Subjects/Inclusion-Exclusion Criteria:**

Subjects (N = 50) will be healthy adults with age +/≥18 years and will be recruited from Duke University along with local community members. Subjects must verbally confirm the absence of any pre-existing skin conditions, skin allergies to tegaderm or other adhesive products contained within the study and control rings and pregnancy.

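### The domestic–Tanzanian ring comparison can show that two preparations differ, but not that regions differ, unless several independent batches represent each region and are accounted for in the analysis

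*Protocol*

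**What the plan says.** Design and Procedures describes two beeswax-pine rings per subject, "one being a domestic beeswax-pine sample while the other ring will be a Tanzanian beeswax-pine sample", worn beside a commercial control ring. It then states what this arrangement can do: "Using both a domestic and international sample, we can test whether regional differences in these products might yield significantly different results".

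On the make-up of the rings, the same section fixes the dimensions and the wax-to-resin proportion: "The beeswax-pine buffer will be composed of the same beeswax-pine resin ratio that will be used in the LowCostomy appliance's overall design". It does not say how many batches, lots or suppliers provide the domestic rings or the Tanzanian rings.

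The number of subjects is given under Selection of Subjects: "Subjects (N = 50) will be healthy adults". The analysis described at the end of Design and Procedures is to be "appropriate statistical analysis will be completed to evaluate for significant differences between each of the samples applied to subjects' skin".

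Purpose of the Study defines safety against the commercial product, as "no greater external skin irritation or injury compared to standard commercially available ostomy appliance products". Region plays no part in that definition.

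**The concern.** Region is a property of the material, so a test of region needs several independent pieces of material from each region. The protocol describes replication only over subjects. If all domestic rings come from one preparation and all Tanzanian rings from another, whatever sets those two preparations apart (the particular wax, the particular resin, how each was made) appears as the domestic–Tanzanian difference. Subjects can show precisely that the two preparations differ, but not why.

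Two readings of the result are at stake. A significant difference could be credited to, or held against, a region's supply when it belongs to one batch. A null result could be taken to cover material from a region that was never sampled. Both ingredients are described as natural products, so some variation within a region is plausible, although the protocol gives no figure for it.

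This is not a matter left open for a statistical analysis plan. The protocol itself states what the design can test, and no analysis can supply replication that the material lacks.

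**Working it through.** **What the protocol supplies.** One ring of each source per subject and N = 50. It gives no significance level, test, variance or number of batches for this comparison, so there is no stated figure to reproduce. What follows is an illustration.

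**Assumptions (not in the protocol).** Two-sided paired test at 5%; no true regional effect; one batch per source; normally distributed differences; all 50 subjects analysed. Let r be the between-batch SD divided by the SD of the within-subject difference. Its value is unknown, so a range is shown.

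**Model.** In units of the within-subject SD, the mean domestic-minus-Tanzanian difference has variance 1/n from subjects and 2r² from the two batches. The paired test uses only 1/n. Hence

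P(significant) = 2 × Φ(−1.96 / √(1 + 2nr²)).

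**Results for n = 50.**

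| r | 1 + 2nr² | 1.96 / √(1 + 2nr²) | P(significant) |
|---|---|---|---|
| 0 | 1 | 1.960 | 5% |
| 0.05 | 1.25 | 1.753 | 8% |
| 0.10 | 2 | 1.386 | 17% |
| 0.25 | 7.25 | 0.728 | 47% |
| 0.50 | 26 | 0.384 | 70% |

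Simulated t-tests under the same model agree closely: about 16%, 46% and 69% at r = 0.10, 0.25 and 0.50.

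**More subjects.** At r = 0.25 the term 1 + 2nr² is 7.25, 13.5 and 26 for n = 50, 100 and 200, giving 47%, 59% and 70%. A larger sample shrinks 1/n but leaves 2r² untouched, so the false-positive rate for a regional claim rises.

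**Several batches that the analysis ignores.** Simulation at r = 0.25 and n = 50, with k independent batches per source spread evenly over subjects and the same paired t-test, gives about 46%, 31%, 17% and 10% for k = 1, 2, 5 and 10. Several batches reduce the problem, but a few batches left out of the analysis do not remove it.

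**The case against.** The strongest objection is that the protocol does not say there is only one batch per source. In the sentence on the two rings, the count is of rings worn by each subject. Fifty subjects need at least 50 rings of each source, and these could come from several batches. This stands. A reader might infer that region and batch are necessarily inseparable in this trial, but the protocol neither states nor rules out single sourcing, so the confounding is conditional.

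It can also be said that the percentages are not specific to this trial. This stands too. Every r is assumed, the lower end of the range is 5% to 8%, and the outcome is a graded Draize score for which many paired differences may be zero. The figures show how an unreplicated source behaves, not the size of an error here.

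A third point is that the regional idea is one sentence with no endpoint or decision attached, and that the analysis text already speaks of differences between samples. That limits the importance of the point. It also shows that the sentence is out of line with the planned analysis, and that rewording would bring the two together.

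Finally, a reader might infer that Tanzanian material is what patients will use, so that a misread null result bears directly on product safety. The protocol does not say this. It names Sub-Saharan Africa as the setting and mentions Tanzania only as the origin of one sample.

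**Conclusion.** The point holds in conditional form. The protocol claims a test of regional differences but describes no replication of suppliers or batches within a region. Unless several independent batches represent each region and are accounted for, a significant result supports only a difference between the two preparations tested, and a null result says nothing about other material from either region.

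The protocol gives no basis for sizing the effect. Under the assumed single-batch model the false-positive rate runs from the nominal 5% to 70% over the range shown.

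The point is minor. The domestic–Tanzanian contrast is secondary, and the main question, irritation against the commercial control, does not require region to be separated from batch.

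**What to change.** Reword the sentence in Design and Procedures, and the planned conclusion, so that they compare the two specific preparations tested and not their regions. Record the batch of every ring, since batch identity may not be recoverable later.

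If several batches per source are used, state how many and spread them evenly over subjects. Make a regional claim only if batch, nested within source, is treated as a source of variation in that comparison. Adding a batch term without saying how it is handled is not enough: as a fixed effect nested in source it leaves no separate source contrast without a further constraint, and as a random effect it is poorly estimated from a few batches.

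The cost is a change of wording and one data field, with no additional subjects. The downside is that the regional claim becomes narrower.
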